Population and Setting: We will randomize up to 250 MVAHCS patients in a ratio of 2:1 intervention: control. Inclusion Criteria (EHR):

- 1) Adults >=18 participating in care, defined as a primary care or pulmonary visit within the past 2 years.
- 2) Past-year smoking status in the electronic health record defined by health factors indicating current smoking (Via validated VA algorithm)
- 3) ICD-10 diagnoses of COPD within the past 2 years
- 4) Not already enrolled in VA tobacco treatment (pharmacist treatment, tobacco groups, mental health tobacco treatment). Patients taking only tobacco cessation medications without counseling will be included.
- 5) Not enrolled in hospice
- 6) No diagnosis of advanced dementia

Exclusions (phone eligibility assessment):

- 1) Unable to communicate by phone in English
- 2) No text-capable phone
- 3) Already guit smoking
- 4) Already participating in tobacco treatment program (note: if using OTC meds without counseling, will not be excluded)
- 5) Decline to be in study but would prefer to receive care coordination immediately

Eligibility, Sampling and Recruitment: We will screen and enroll patients who meet the eligibility criteria, applying the above criteria initially using the EHR, confirming criteria during phone contact. Patients will be randomized irrespective of their intention to quit smoking.

Women and Racial Minorities: To increase representation of these groups, we will oversample eligible women and racial/ethnic minority patients with a goal of 14% female patients and 24% minority patients invited to participate.

Study Procedures:

[figure not shown]
Screening: Research coordinator will screen patients for possible eligibility using a secure electronic application located behind the VA firewall.

Invitation: Study is minimal risk and will be conducted under a waiver of HIPPA and documentation of informed consent. Eligible participants will be sent an "opt out" letter that describes the study and contains the necessary elements of informed consent. Eligible patients will have the opportunity to opt out at this time by calling the study team.

Recruitment: Patients will be recruited by phone starting 1 week after letter is

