mailed. Patients will be called up to 6 times at different times of the day to make contact. Once contacted, research coordinator (RC) will confirm eligibility and obtain verbal consent to study procedures. For consenting patients. RC will administer the baseline survey and verbally consent them to participation in the VA "Annie" program and motivational texting program. Documentation of verbal consent to Annie participation is required by the VA Office of Connected Care. Annie consent language has been approved by MVAHCS representative ([name], MvHealtheVet coordinator). Verbal consent will be documented in CPRS in a Research Participant Note utilizing the "Annie Consent"

Figure 1: Study flow diagram of the randomized pilot evaluation

template. Patients who decline to complete baseline and immediately have care coordination will be considered ineligible. PCP and PACT pharmacist will be notified by co-signature to a research participant note.

Baseline Assessment:

Phone survey will assess: current tobacco use, motivation to quit, prior quit experiences, use of technology, and severity of shortness of breath. See table of measures. Charlson comorbidity index and history of mental health diagnoses will be pulled from the CDW.

Annie Enrollment:

All consenting participants will be enrolled in the VA "Annie App" and will receive an initial text message informing them of this enrollment. The Annie App is the VA's text-message-based health promotion platform used to provide education, self-management and clinical protocols. Participants will need to reply once to this message to confirm enrollment. Participants already enrolled in the Annie App will have this participation confirmed in the Annie portal.

Randomization:

Consenting participants will be randomized 2:1 to the intervention versus usual care using the enrollment application. To maintain balance in race and gender, randomization will be stratified by these characteristics; within strata, randomization will employ randomly permuted balanced blocks of size 2, 4, and 6.

Proactive Protocol V2.1 11/20/23

Usual Care:

Participants in the usual care arm will be managed per usual as directed by their medical team.

Intervention:

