Cost Analysis: We will prospectively capture information on cost associated with performing the proactive tobacco treatment intervention. To estimate the cost associated with implementation, we will capture time spent building any templates and electronic tools, and training staff. To estimate cost associated with staffing the program once it is created, for one month during the pilot, all study staff will enter daily the time spent in the clinical tasks associated with delivering the intervention into a spreadsheet, excluding activities that are related only to research administration. To estimate cost related to an increase in use of tobacco treatments attributable to the program, we will estimate the difference in use of tobacco treatments in addition to the intervention-related costs.

Measurements and Data Source:

See Table 1 for full list of measurements and data sources.

Table 1: Measures	
Measures	
Baseline Measures	
Survey	Demographics: Age, gender, race, ethnicity, education, income, health literacy Health Measures: Self-reported health, respiratory symptoms questionaire, diagnosis of COPD, Audit-C Access to Technology: Access to devices, access to internet, use of e-mail, use of secure patient portal, frequency of texting, electronic health literacy scale Tobacco Measures: current tobacco product use, heaviness of smoking index, past-year quit attempts and use of cessation resources, ever use of cessation resources, quit confidence scale, motivation to quit, intention to quit

EHR	Charlson comorbidity index, mental health diagnoses	
Outcome Measures		
Study Recorded and EHR	Response to the program (via telephone, via Annie App), timing of response to program, Acceptance of referral, choice of referral program, cessation medications (varenicline, bupropion,	
ENK	nicotine replacement single/combination), documented tobacco treatment visits (pharmacist, class, mental health, primary care) or warm handoff to quitline	
Survey	Primary outcome: Use of any tobacco treatment	
	Secondary Outcomes: Use of combination treatment (behavioral + pharmacotherapy), individual	
	treatment choice (program, medications), heaviness of smoking, quit attempts (y/n and number),	
	7 day and 30 day abstinence, Stage of change, quit confidence	
	Additional Outcomes: Acceptability of text messaging program, feedback on messages,	
	agreement to qualitative interview	

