Annie App	Opted out (y/n), number of messages received, Participant responses received through the app	
Cost Measures		
Staff recorded	Program-associated costs: hours/week for patient identification, number of weekly phone calls,	
	average call duration, time spent coordinating care, technology costs (patient identification	
	queries, development of eligibility app)	
	Treatment-associated costs : medication costs, pharmacy processing costs, average number, type	
	and duration of counseling visits (groups, quitline, pharmacist counseling, tobacco-related primary	
	care visits, mental health treatment)	
Abbas detisas CODD	-phronia abatruativa nulmanary diagga. EUD: Electronia Haalth Boord	

Abbreviations: COPD=chronic obstructive pulmonary disease, EHR: Electronic Health Record

Analysis Plan:

We will perform descriptive analysis of the demographic and health history measures to describe the participants in the study overall, and in each study arm, as well as by outreach contact and receipt of any treatment and combination behavioral and pharmacological treatment. We will also summarize these measures by gender and race. Our primary aim is to assess the feasibility of implementing a larger trial of the electronic patient engagement intervention. Our primary focus then will be estimating rates, along with 95% confidence intervals, of outreach contact and treatment referral in the text outreach arm and of receipt of any and combination behavioral and pharmacological treatment in each study arm; additional analyses will weight observations by sample inclusion probabilities according to gender and race so that sample results are reflective of the overall population. While the study is not powered for detecting differences in cessation, we will explore potential differences in cessation between the two arms using likelihood ratio chi-square tests.

In addition to the descriptive information on the composition of the study population, we will identify the characteristics of those who respond, receive cessation treatment and those who attain abstinence in each arm, again assessing significance of differences in outcomes using logistics regression analyses and likelihood ratio chi-squared tests. This information will be valuable for planning a future study comparing the electronic proactive outreach intervention with previous studies of phone outreach. We will also descriptively analyze the Annie data to further tailor the protocol.

Power and Sample Size:

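### No covariate-adjusted arm difference is prespecified, although objective 1 is to estimate effect size and prognostic tobacco measures are collected at baseline

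*Combined protocol and SAP*

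**What the plan says.** Under Population and Setting: "We will randomize up to 250 MVAHCS patients in a ratio of 2:1 intervention: control". Under Eligibility, Sampling and Recruitment: "Patients will be randomized irrespective of their intention to quit smoking". Under Randomization: "To maintain balance in race and gender, randomization will be stratified by these characteristics". No tobacco measure is a stratification factor.

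The baseline survey in Table 1 includes "current tobacco product use, heaviness of smoking index" and "quit confidence scale, motivation to quit, intention to quit". Heaviness of smoking and quit confidence appear again in Table 1 as secondary outcomes at 6 months.

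Table 1 gives "Primary outcome: Use of any tobacco treatment". For it, the Analysis Plan promises rates with 95% confidence intervals "of receipt of any and combination behavioral and pharmacological treatment in each study arm", and defines no between-arm estimator. For cessation, which the plan says it is not powered to compare, "we will explore potential differences in cessation between the two arms using likelihood ratio chi-square tests". The next paragraph names logistic regression, but to identify the characteristics of those who respond, are treated or become abstinent in each arm. It lists no covariates and no arm term.

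Study Objectives nonetheless includes estimating effect size in the first objective, and the Cost Analysis text under the study procedures relies on a difference in treatment use attributable to the program.

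**The concern.** Because intention to quit is not an entry filter, participants will range from those ready to quit to those who are not. The protocol's own rationale names nicotine addiction and low motivation as barriers to cessation, so the baseline tobacco measures can be expected to predict treatment use and abstinence. Randomization balances them only on average. If the arms happen to differ on one of them, an unadjusted difference carries that imbalance and the reader has no prespecified analysis that accounts for it. Leaving adjustment open also allows the choice between adjusted and unadjusted results to be made after the imbalance is seen.

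At stake is the precision of the effect estimate that the pilot hands to a larger trial and to its own cost estimate. Neither the validity of the comparison nor the feasibility rates are in question.

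**Working it through.** **Inputs from the protocol.** Maximum 250 patients at 2:1, so about 167 and 83; stated standard errors of 3.9% and 5.4% (Power and Sample Size). The protocol gives no outcome rates, covariate prevalences or covariate effects. All of these below are assumptions, shown as ranges, and every figure takes the full 250 with complete follow-up.

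**The plan's own figure.** SE = sqrt(p(1−p)/n) at p = 0.5.
- n = 167: sqrt(0.25/167) = 3.87%, stated as 3.9%.
- n = 83: 5.49%; n = 84: 5.46%; stated as 5.4%. This is a rounding matter with no bearing here.
- The two stated figures imply an SE for the arm difference of sqrt(3.9² + 5.4²) = 6.7 points at a 50% rate, a number the plan does not give.

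**Chance imbalance.** For a binary trait with prevalence q, SD = sqrt(q(1−q)(1/167 + 1/83)), where 1/167 + 1/83 = 0.01804.

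| q (assumed) | SD of imbalance | P(imbalance above 10 points) |
|---|---|---|
| 20% | 5.4 points | 6% |
| 30% | 6.2 points | 10% |
| 50% | 6.7 points | 14% |

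For a continuous measure the SD of the imbalance is sqrt(0.01804) = 0.13 SD, with a 95% range of about ±0.26 SD.

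**Effect on the risk difference.** Shift = imbalance × risk difference associated with the covariate. Take that as 10 to 30 points and q as 30% to 50%.
- 1-SD imbalance: 0.0615 × 0.10 = 0.6 points up to 0.0671 × 0.30 = 2.0 points.
- 1.96-SD imbalance: 1.2 to 3.9 points.
- Unadjusted SE at a pooled rate of 25%: sqrt(0.1875 × 0.01804) = 5.8 points.
- Share of variance due to one such covariate, (1-SD shift / SE)²: 1% to 12%.

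**Simulation of adjustment.** 1,500 trials per scenario at 167:83, with three independent standard-normal covariates. The unadjusted analysis was compared with a standardized risk difference from a logistic model.

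| True rates | Log-OR per SD, each covariate | Variance ratio, unadjusted/adjusted | Power, unadjusted to adjusted |
|---|---|---|---|
| 20% v 35% | 0.2 / 0.4 / 0.6 | 1.02 / 1.10 / 1.16 | 71→72% / 71→75% / 73→79% |
| 8% v 16% | 0.2 / 0.4 / 0.6 | 1.00 / 1.04 / 1.12 | 47→49% / 47→47% / 43→49% |

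The variance saved is 1 − 1/ratio: from 0% (ratio 1.00) to 1 − 1/1.16 = 14%. With 8% in both arms and the weakest effects the ratio was 0.98, so adjustment can cost a little when events are few and covariates weak.

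The unadjusted estimate was unbiased (mean 0.148 to 0.152 for a true 0.15), with 94% to 95% coverage and type I error of 4% to 5%.

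**Outcomes with their own baseline.** In a linear model with the baseline value as covariate, variance falls by the squared correlation: 0.5² = 25%, 0.6² = 36%.

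**Events for abstinence.** At 8% v 16%: 0.08 × 83 + 0.16 × 167 = 6.6 + 26.7, or about 33 quits. Some adjusted fits in the simulation gave convergence warnings.

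**The case against.** The strongest reply is that this is a feasibility pilot. Its primary focus is rates within arms, the test at issue is declared exploratory and underpowered, and differences in enrollment and cessation are left to future research. The larger gap is arguably that no between-arm estimator exists for the primary outcome at all, and adjustment only refines it. The gain is also small on most assumptions: about 90% of trials stay within 10 points on a 30% covariate, and power rises by 6 points at most. All of that stands and limits the weight of the point. It does not remove it, because objective 1 and the cost analysis both need an arm difference and the covariates are already in hand.

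Three stronger readings are tempting, and the documents do not support them.

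- A reader might infer that the effect estimate is biased. It is not: the allocation is randomized, and the unadjusted confidence interval already allows for chance imbalance, as the simulation shows.
- A reader might infer that baseline characteristics are ignored altogether. Logistic regression on characteristics is planned, and Power and Sample Size foresees stratifying uptake on key variables. Neither is described as an adjusted arm effect.
- A reader might infer that the program's motivational target lacks a matching baseline, because Table 1 lists stage of change at follow-up instead of motivation and intention. The Intervention section gives the aim as more quit attempts and more participation in treatment, and Table 1 collects both kinds of measure at baseline and follow-up. The survey items are not in the documents, so whether stage of change corresponds to the intention item cannot be settled. No added survey items are needed on this ground.

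**Conclusion.** The point holds as a low-cost improvement. The plan prespecifies no adjusted arm difference, and its one named arm comparison omits both the stratification factors and the prognostic baseline measures. The analysis as written remains valid.

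For treatment use and abstinence the gain is modest, about 0% to 14% of variance with three covariates of log-OR 0.2 to 0.6 per SD at the assumed rates. It is largest for heaviness of smoking and quit confidence, at 25% to 36%, but only if the baseline correlation is 0.5 to 0.6. No covariate effect or correlation is given in the documents, so the direction of these gains is better supported than their size.

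**What to change.** In the Analysis Plan, add text to this effect:

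- **Any and combination treatment:** report the arm difference as a standardized risk difference with 95% CI from a logistic model with arm, race, gender and a short fixed list of baseline tobacco measures, for example intention to quit and motivation. Standardizing keeps the result on the same scale as the per-arm rates already planned. Report the unadjusted difference beside it.
- **Abstinence:** use arm and one or two covariates named in advance, since events may be few. Report the unadjusted difference as well.
- **Heaviness of smoking and quit confidence at 6 months:** adjust each for its own baseline value, and state how heaviness is scored for participants who have stopped smoking.
- **Missing baseline items:** state a rule, because participants may skip questions and should not drop out of the model for that reason.

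The covariate list should be fixed before outcome data by arm are seen. The cost is a paragraph in the plan and a few lines of code, with no new patients, procedures or survey items.

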A sample size of approximately 167 participants in the intervention arm will be sufficient to estimate rates of contact, referral, and enrollment in behavioral and pharmacologic treatment with a precision (standard error) of +/- 3.9% and the control arm of 5.4%, which will be informative for planning future research. However, if feasible we will continue recruitment to attain more precision. Similarly, we will be able to estimate eligible population sizes, outreach connection rates, referral rates, rates of behavioral treatment enrollment and rates of pharmacologic treatment separately, and related facets of the intervention delivery to within similar degrees of precision. We will have enough variation in patient characteristics to stratify uptake on key variables, including age and disease severity. We may not have sufficient power to determine a statistically significant increase in enrollment in behavioral and pharmacologic treatment or smoking cessation, but these will be examined as aims of future research.

Cost Analysis: Estimates of time and workload for each staff member and clinical role involved in implementing and staffing the program will be combined with regional VA salary information to generate total costs for the proactive program. We will combine this also with regional estimates of pharmacy costs and the prevalence of

COPD and tobacco use at the MVAHCS to produce an overall estimate of cost for the program should it be implemented for the total population.

Qualitative Analysis: Transcribed interviews and notes will be analyzed using directed content analysis with NVIVO software, with constructs based on the technology adoption model and the consolidated framework for implementation research.

Expected Outcomes and Deliverables:

We expect that an electronic proactive patient engagement program will be feasible and will result in more patients enrolling in tobacco treatment. We also expect variation in response to the program by age and baseline technology use. We expect to find that the budget impact of the intervention itself is small and that most of the increase in cost will be due to increased utilization of existing quit resources.

Informed Consent

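### The between-arm cessation comparison rests on an unstratified likelihood ratio chi-square test alone, with no effect estimate or interval; a stratified risk difference with a Cochran-Mantel-Haenszel test would serve better at almost no cost (minor)

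*Combined protocol and SAP*

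**What the plan says.** The trial is a 2:1 randomised pilot: "We will randomize up to 250 MVAHCS patients in a ratio of 2:1 intervention: control". Under Randomization, the balancing factors are race and gender: "randomization will be stratified by these characteristics; within strata, randomization will employ randomly permuted balanced blocks of size 2, 4, and 6".

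The Analysis Plan makes estimation its main task, but the 95% confidence intervals that it lists are for rates of contact, referral and receipt of treatment. Cessation is handled differently. The plan concedes the lack of power ("While the study is not powered for detecting differences in cessation") and then says "we will explore potential differences in cessation between the two arms using likelihood ratio chi-square tests". Nothing else is named for the arm comparison of cessation: no effect measure, no interval, no stratification and no rule for sparse tables.

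The next paragraph looks within each arm at the characteristics of those who respond, are treated or become abstinent, "again assessing significance of differences in outcomes using logistics regression analyses and likelihood ratio chi-squared tests".

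No significance level is given for any test, and no expected quit rate or dropout rate is given anywhere.

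**The concern.** The likelihood ratio statistic is referred to a chi-square distribution, and that approximation can be poor when few people quit. An example at the planned size: 5 quitters in the intervention arm and none in control gives G = 4.09 (p = 0.043), while Pearson's statistic is 2.54 (p = 0.11). Yet if 5 people quit in total and treatment does nothing, all 5 fall in the larger arm with probability close to (2/3)^5 = 13%.

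Low counts are possible here. Abstinence is to be confirmed by exhaled carbon monoxide using a device that connects to a smartphone, whereas eligibility requires only a text-capable phone.

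The second issue is separate. The trial balances on race and gender but does not plan to analyse by them, and a bare p-value for cessation gives the designers of the next trial no effect size or range to plan from. What is at stake is how useful and reliable an exploratory result is, not the trial's main conclusion.

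**Working it through.** **Inputs.** Arm sizes of 167 and 83 come from 250 at 2:1 and from Power and Sample Size ("A sample size of approximately 167 participants in the intervention arm"; control by subtraction). The gender and race shares of 14% women and 24% minority are the protocol's goals for patients invited; carrying them through to enrolment is an assumption. Also assumed: a two-sided 5% level (cut-off 3.841 on 1 df), a range of quit rates, and a range of missing data.

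**The plan's own figure.** SE = sqrt(p(1-p)/n) at p = 0.5. For n = 167 this is 3.87% (stated 3.9%). For n = 83 it is 5.49% (stated 5.4%, which matches if truncated). The arm sizes are therefore as read.

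**Step 1: size of the between-arm test.** G = 2 Σ O ln(O/E), with rejection if G > 3.841. The size is the total probability of all rejecting pairs of counts when both arms share one quit rate, by full enumeration of two binomials.

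| Quit rate | Expected quitters, total | LR, 167 v 83 | Pearson, 167 v 83 |
|---|---|---|---|
| 1% | 2.5 | 5.3% | 4.1% |
| 2% | 5.0 | 8.0% | 3.8% |
| 3% | 7.5 | 7.7% | 4.1% |
| 4% | 10.0 | 6.4% | 4.4% |
| 5% | 12.5 | 5.7% | 4.5% |
| 8% | 20.0 | 5.4% | 4.6% |
| 10% | 25.0 | 5.2% | 4.7% |
| 20% | 50.0 | 5.1% | 5.0% |

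The likelihood ratio peak is 8.2% at a quit rate of 2.4%, where the control arm expects 83 × 0.024 = 2.0 quitters. Missing data move the window to higher rates: with 30% missing (117 v 58) the size is 7.8% at 4% and 6.8% at 5%; with 40% missing (100 v 50) it is 7.4% at 5% and 5.5% at 10%.

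**Step 2: within-arm tables, if run.** Applying the invitation goals: 167 × 0.14 ≈ 23 and 83 × 0.14 ≈ 12 women; 167 × 0.24 ≈ 40 and 83 × 0.24 ≈ 20 minority patients.

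| Table | LR near its peak | LR elsewhere |
|---|---|---|
| Women v men, intervention (23 v 144) | 7.9% at 8%, 8.5% at 10% | 3.8% at 2%, 2.5% at 4%, 5.4% at 15% |
| Minority v not, intervention (40 v 127) | 8.2% at 5%, 8.0% at 6% | 6.7% at 8% |
| Minority v not, control (20 v 63) | 8.1% at 10%, 7.6% at 12% | 2.0% at 2%, 4.1% at 5%, 5.3% at 20% |
| Women v men, control (12 v 71) | 8.1% at 15%, 8.3% at 20% | 3.3% at 5%, 2.7% at 8% |

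At these peaks the smaller group expects about two quitters (23 × 0.10 = 2.3; 40 × 0.05 = 2.0; 20 × 0.10 = 2.0; 12 × 0.20 = 2.4). The logistic regression also planned is no safeguard: its likelihood ratio test for one binary predictor is the same G statistic.

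**Step 3: effect of the strata.** Simulation under no treatment effect, 250 patients, gender × race strata, 2:1 blocks. Blocks of 3 and 6 were assumed, because the stated sizes 2 and 4 cannot hold a 2:1 ratio (a separate matter to reconcile).

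| Quit rates across strata | Unstratified LR | CMH |
|---|---|---|
| 10% in all | 5.3% | 4.8% |
| 8-20% (mean 10%) | 5.0% | 4.8% |
| 5-50% (mean 13%) | 3.8% | 5.0% |

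At one common rate of 5%, a run of 20,000 trials gave 6.1% for LR and 4.9% for CMH; a repeat with 100,000 gave 5.7% and 4.6%. In a further simulation with equal rates from 2% to 15%, CMH stayed between 3.7% and 4.9%.

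**The case against.** The case against is substantial.

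- **The comparison is exploratory.** It is declared unpowered, no decision rule hangs on its p-value, and the stated focus is estimation of rates. This stands, and it sets the severity.
- **No 5% level is stated.** Correct. The documents commit to no error rate that could be breached; 5% is a yardstick assumed here.
- **The excess is confined to a narrow window.** With full data, about 8% needs roughly 5 to 8 quitters in total, and no quit rate in the documents places the trial there. This stands for the arm comparison.
- **Within-arm gender and race tables are inferred.** The plan does not say which characteristics are tested or by which method. This stands, so those figures are conditional.
- **Pearson's test is not uniformly better.** At 12 v 71 and a 2% quit rate its size is 6.5%, against 6.0% for LR; at 23 v 144 and 2% it is 5.6%, against 3.8%. This stands, and it is why an exact or mid-P method is preferred for sparse within-arm tables.

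A reader might infer that ignoring the strata is part of why the test over-rejects. The simulation shows the reverse: ignoring strata that predict quitting is neutral to conservative. A reader might also infer that the pilot will over-report cessation signals. That does not follow either, since the same within-arm tables run at 2-4% at other plausible quit rates.

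None of this answers the remaining point: the plan offers only an unstratified p-value where a stratified estimate with an interval is available at no real cost.

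**Conclusion.** The point holds as a minor one. For between-arm cessation the plan names an unstratified likelihood ratio chi-square test and nothing more. Under an assumed two-sided 5% level and complete data, its size is about 8% at a 2-3% quit rate, 5.7% at 5%, and at most 5.2% from 10% upwards. Within-arm tables can reach about 8% at some quit rates from 5% to 20% if enrolment matches the invitation goals, and fall well below 5% at others.

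The inflation comes only from the chi-square approximation at small counts. The unused strata are a separate weakness that costs efficiency: about 3.8% against 5.0% for CMH in the most uneven scenario examined, and almost no difference when rates vary little. The documents do not support saying that error rates will be inflated in this trial, only that the named test does not guard against it if quitters turn out to be few.

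**What to change.** In the Analysis Plan, replace the cessation sentence with something like:

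> Cessation will be compared between arms, as an exploratory analysis, by the Mantel-Haenszel risk difference with its 95% confidence interval, stratified by gender and race, with the Cochran-Mantel-Haenszel test (two-sided). For comparisons of characteristics within an arm, any table with an expected count below 5 will be analysed by an exact or mid-P test.

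State the significance level used as a reference, and define the race categories so that they match those used to randomise. Some strata will be small: women from minority groups would number about 250 × 0.14 × 0.24 ≈ 8 if the two shares are independent. The Mantel-Haenszel method tolerates such strata, but one with patients in only one arm contributes nothing. Coverage of the interval at very low counts was not checked here; a stratified score interval is an alternative.

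The cost is two sentences and standard software, with no change to design, data collection or sample size. The downside is that p-values may be slightly less favourable when counts are low. The change should be made before outcome data are examined.

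### Testing characteristics arm by arm, with no arm-by-characteristic term, cannot support contrasts between the arms, and abstinence in the small control arm may be too sparse for ordinary logistic regression

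*Combined protocol and SAP*

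**What the plan says.** The relevant sentence is in the second paragraph of the Analysis Plan. It promises that "we will identify the characteristics of those who respond, receive cessation treatment and those who attain abstinence in each arm". The method named for this is significance testing by logistic regression and likelihood ratio tests. The next sentence gives the use: "This information will be valuable for planning a future study". No list of characteristics, model form, interaction term or sparse-data method is stated there or elsewhere.

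Three other places bear on the point. The first paragraph of the Analysis Plan makes rates with 95% confidence intervals the primary focus and adds "While the study is not powered for detecting differences in cessation, we will explore potential differences in cessation between the two arms". Power and Sample Size expects enough variation to stratify uptake on key variables, naming age and disease severity. Expected Outcomes and Deliverables states "We also expect variation in response to the program by age and baseline technology use".

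**The concern.** Two separate sets of tests, one per arm, invite the reader to compare them: a characteristic significant in the texting arm and not under usual care looks like one that the program acts on. That comparison is unsound. Whether a test reaches significance depends on arm size and event count as well as on the association, and here one arm is twice the size of the other. A direct estimate of the difference needs both arms in one model with an interaction.

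A second problem concerns abstinence. If few control participants quit, an uncommon characteristic may have no quitters at all, and the maximum-likelihood odds ratio is then zero or infinite.

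At stake is the input to the next trial. The protocol intends to use these results for planning, and chance one-arm findings could steer its choice of target population or tailoring.

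**Working it through.** **Inputs.** Population and Setting: "We will randomize up to 250 MVAHCS patients in a ratio of 2:1 intervention: control". Power and Sample Size puts about 167 in the intervention arm, so control is 250 − 167 = 83. The 14% share of women is the goal for those invited, and I assume it carries over to those randomised. No significance level is stated for these tests, so I assume 5% two-sided. No treatment or abstinence rate is given, so I use ranges.

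**1. The plan's own figure.** At p = 0.5 the standard error is √(0.25/167) = 3.87% (stated 3.9%) and √(0.25/83) = 5.49% (stated 5.4%). The gap in the second is under 0.1 point and immaterial. The arm sizes are confirmed.

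**2. Significance in one arm only, with no true difference.** Take a characteristic present in half of participants (q = 0.5) with a true odds ratio of 2 in both arms. In an arm of size n with outcome rate p, the approximate standard error of the log odds ratio is √{1/[n p(1−p) q] + 1/[n p(1−p)(1−q)]}. Power is Φ(ln 2/SE − 1.96) plus a negligible opposite tail. The arms are independent, so the chance of significance in exactly one is P_c(1 − P_i) + P_i(1 − P_c).

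| Assumed rate, control / intervention | SE, control / intervention | Power, control / intervention | Exactly one arm |
|---|---|---|---|
| 10% / 15% | 0.732 / 0.433 | 0.16 / 0.36 | 0.40 |
| 15% / 25% | 0.615 / 0.357 | 0.20 / 0.49 | 0.50 |
| 30% / 40% | 0.479 / 0.316 | 0.30 / 0.59 | 0.54 |

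First row: 0.16 × 0.64 + 0.36 × 0.84 = 0.40. The last column uses unrounded powers.

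**3. What an interaction term could show.** Its standard error is √(SE_c² + SE_i²). In the second row this is √(0.378 + 0.128) = 0.711, and power for a ratio of odds ratios of 2 is Φ(0.693/0.711 − 1.96) = 16%. The range runs from 8% (14% prevalence, rates 10%/15%) to 25% (50% prevalence, rates 50%/50%).

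**4. Sparse data for abstinence.** Control women: 0.14 × 83 ≈ 12. Intervention women: 0.14 × 167 ≈ 23. The chance that none quits is (1 − p)^12 or (1 − p)^23.

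| Assumed abstinence | Control events | No quitters among 12 control women | Intervention events | No quitters among 23 intervention women |
|---|---|---|---|---|
| 5% | 4 | 54% | 8 | 31% |
| 10% | 8 | 28% | 17 | 9% |
| 15% | 12 | 14% | 25 | 2% |

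Non-response to the 6-month survey would lower these counts further; the documents give no rate.

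**5. Treatment use.** At assumed rates of 25-50% there are 21-42 control events (0.25 × 83 to 0.50 × 83) and 42-84 intervention events. The chance that none of 12 control women is treated is 0.75^12 = 3% at 25% and smaller above that.

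**The case against.** The best defence is that the plan promises less than it is being held to. Within-arm logistic regression does estimate within-arm associations, and the likelihood ratio statistic stays finite when the odds ratio does not. The analysis is exploratory, sits in a feasibility pilot, and carries an explicit disclaimer on power for cessation. All of that stands, and it limits the severity.

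A reader might go further than the documents allow in four ways.

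- **That the plan claims to show who benefits.** It does not. The stated use is planning, and the expected variation in response may simply mean replying to the texts. Table 1 records response by telephone or through the app, which arises only in the intervention arm. On that reading a one-arm description is right and no interaction can be fitted.
- **That treatment use, the primary outcome, is also too sparse.** No rate is given, and step 5 shows adequate counts for single-predictor models over a plausible range.
- **That every baseline measure in Table 1 will be tested or entered jointly.** The plan says neither, so no total of tests or ratio of events to predictors can be held against it.
- **That pooling sharpens the within-arm odds ratios.** Without other covariates, an interaction model reproduces the separate-arm odds ratios and standard errors. Its gain is a direct estimate of the contrast. Only the penalty deals with zero cells.

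The phrase about differences in outcomes could also cover comparisons between arms. The within-arm reading is the more natural one, since the preceding paragraph already deals with cessation between arms.

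**Conclusion.** The concern holds as a minor one. Tests within each arm, with no interaction, cannot support a statement that a characteristic matters differently under the texting program. With a common odds ratio of 2, a one-arm-only result would arise about 40-54% of the time. This applies to treatment receipt and abstinence alike. It rests on the Wald approximation, a characteristic split evenly, a 5% level and assumed outcome rates of 10-40%.

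Infinite odds ratios are a real risk only for abstinence, mainly in the control arm and for uncommon characteristics: 54%, 28% or 14% for control women at assumed quit rates of 5, 10 or 15%. The within-arm estimates are not wrong in themselves, and the primary rate estimates do not depend on this analysis. What is available is a better method on the same data.

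**What to change.** Replace the sentence in the Analysis Plan with the following specification.

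- For treatment receipt and abstinence, fit a pooled logistic model with arm, the characteristic and their interaction, adjusted for the randomisation strata (gender and race).
- Do this for a short list fixed in advance, such as age, baseline technology use and disease severity, all of which the protocol already names. State which Table 1 measure represents each of the last two.
- Use Firth-penalised likelihood for abstinence.
- Report the within-arm odds ratios and the interaction as exploratory estimates with 95% confidence intervals, and drop the significance wording.
- Keep response to the texts as a description of the intervention arm.

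The cost is analysis wording only, with no added data or participant burden. The downside is that the interaction will be imprecise (about 8-25% power for a ratio of odds ratios of 2) and fewer nominally significant predictors will be reported. A wide interval is still safer planning input than a p-value from one arm.
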